The sample size re-estimation was to be performed once the primary analysis for the interim had been completed and assuming that no overwhelming data supporting the need to stop for futility was observed. Estimates of standard deviations and within subject correlation were to be obtained from the PASP outputs produced during the interim and/or from SAS outputs from the statistical modelling. The sample size re-estimation was to be performed by re-running programs (using R) used to obtain pre-study precision estimates. The sample size re-estimation program and associated excel outputs of precision estimates were to be archived.

The interim analysis was performed when 11 subjects had been randomised. One subject did not complete both periods 1 and 2 due to withdrawal due to AE, therefore 10 subjects were analysed for the primary endpoint. Following a review of the data, the decision was made to make modifications to the protocol and continue the study (Part 2). Major modifications are a change in the hypoxia chamber altitude from 4000m to 5000m and echo recordings at the T3 timepoint being taken 2 minutes into exercise (due to use of semi-recumbent cycle), rather than at the end of a 10 minute exercise period. Part 1 and 2 of the study will be analysed separately.

3.1.2. Part 2

For Part 2 of the study, up to 14 subjects are planned to be randomised. Two interim analysis reviews are planned as follows:

- Review of PASP, oxygen saturation and AE data when approximately 3 subjects have completed Treatment Periods 1 and 2.
- Review of PASP, oxygen saturation and AE data when approximately 6 subjects have completed Treatment Periods 1 and 2. This second review may not be required and will be dependent on data observed during the first interim review. The timing of this review may be altered, as necessary, dependent on subject recruitment. Further interim reviews may take place, if appropriate.

At each review, the study may be stopped for futility if PASP results are highly variable, or if the PASP profile for the placebo group is not as expected (indicative of the model not working given the alterations to the study) or if review of the safety data suggests a change in the benefit-risk profile. If clear criteria for stopping the study are not met, the study will continue to the next interim analysis review, or on to the planned maximum number of evaluable subjects. Further interim reviews may be performed if deemed appropriate by the study team.

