
 Reporting for tables, figures and formal statistical analyses : 
 Planned time relative to dosing will be used in figures, summaries, statistical analyses and calculation of any derived parameters, unless otherwise stated. The impact of any major deviation from the planned assessment times and/or scheduled visit days on the analyses and interpretation of the results will be assessed as appropriate. Reporting for Data Listings: 
 Planned and actual time relative to study drug dosing will be shown in listings (Refer to IDSL Statistical Principle 5.05.1). Unscheduled or unplanned readings will be presented within the subject's listings. Visits outside the protocol defined time-windows (i.e. recorded as protocol deviations) will be included in listings but omitted from figures, summaries and statistical analyses. 	
Unscheduled Visits	

 Unscheduled visits will not be included in summary tables or figures, unless otherwise stated. All unscheduled visits will be included in listings. 	
Descriptive Summary Statistics	
Continuous Data	Refer to IDSL Statistical Principle 6.06.1
Categorical Data	N, n, frequency, %
Descriptive Summary Statistics (Log Transformed Data)	N, n, geometric mean, 95% CI of geometric mean, standard deviation (SD) of logged data and between geometric coefficient of variation (CV _{b/w} (%)): $CV_b (\%) = \sqrt{(\exp(SD^2) - 1) * 100}$ (NOTE: SD is the SD of log transformed data)
Reporting of Pharmacokinetic Concentration Data	
Descriptive Summary Statistics	Refer to IDSL Statistical Principle 6.06.1 Assign zero to NQ values (Refer to GUI_51487 for further details)
Reporting of Pharmacokinetic Parameters	
Descriptive	N, n, geometric mean, 95% CI of geometric mean, standard deviation (SD)

Reporting Standards	
Summary Statistics (Log Transformed)	of logged data and [between and or within] geometric coefficient of variation (CV _{b/w} (%)) will be reported. [1] $CV_b (\%) = \sqrt{(\exp(SD^2) - 1) * 100}$ (SD = SD of log transformed data) [2] $CV_w (\%) = \sqrt{(\exp(MSE) - 1) * 100}$ (MSE = mean square error from mixed effect model of loge-transformed data).
Parameters Not Being Log Transformed	Tmax, first point, last point and number of points used in the determination of lambda_z for listings

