10.4. Appendix 4: Derived and Transformed Data

10.4.1. General

Multiple Measurements at One Time Point

 Mean of the measurements will be calculated and used in any derivation of summary statistics but if listed, all data will be presented. If there are two values within a time window the value closest to the target day for that window will be used. If values are the same distance from the target then the mean will be taken. Subjects having both High and Low values for Normal Ranges at any post-baseline visits for safety parameters will be counted in both the High and Low categories of “Any visit post-baseline” row of related summary tables. This will also be applicable to relevant Potential Clinical Importance summary tables.
Study Day

 Calculated as the number of days from randomisation date : 
 Ref Date = Missing → Study Day = Missing Ref Date < Randomisation Date → Study Day = Ref Date – Randomisation Date Ref Date ≥ Randomisation Date → Study Day = Ref Date – (Randomisation Date) + 1

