3.20.	mITT1	AE1CP (same as CP_AE1x)	Summary of All Serious Adverse Events by System Organ Class and Preferred Term (Part 1)	Production of this will be dependent on the number of SAEs, listing may suffice (based on clin pharm IDSL standards advice, this is a conditional summary). Summarise by treatment group. Any pre-treatment SAEs to be included only in listing.	SAC
3.21.	mITT2	AE1CP (same as CP_AE1x)	Summary of All Serious Adverse Events by System Organ Class and Preferred Term (Part 2)	As above (Part 2 population)	SAC
ECG					
3.22.	mITT1	EG1	Summary of ECG Findings (Part 1)		SAC
3.23.	mITT2	EG1	Summary of ECG Findings (Part 2)		SAC
3.24.	mITT1	EG2	Summary of ECG Values (Part 1)		SAC
3.25.	mITT2	EG2	Summary of ECG Values (Part 2)		SAC
3.26.	mITT1	CP_EG11	Frequency of ECG Values by Pre-Specified PCI Categories (Part 1)	Categories as per PCI details in Section 10.6.2.	SAC

Safety : Tables					
No.	Population	IDSL / TST ID / Example Shell	Title	Programming Notes	Deliverable [Priority]
3.27.	miTT2	CP_EG11	Frequency of ECG Values by Pre-Specified PCI Categories (Part 2)	As above (Part 2 population)	SAC
3.28.	miTT1	EG2	Summary of Change from Baseline in ECG Values (Part 1)		SAC
3.29.	miTT2	EG2	Summary of Change from Baseline in ECG Values (Part 2)		SAC
3.30.	miTT1	CP_EG12	Frequency of Change from Baseline ECG Values by Pre-Specified PCI Categories (Part 1)	Categories as per PCI details in Section 10.6.2.	SAC
3.31.	miTT2	CP_EG12	Frequency of Change from Baseline ECG Values by Pre-Specified PCI Categories (Part 2)	As above (Part 2 population)	SAC
Vital Signs					
3.32.	miTT1	VS1	Summary of Vital Signs (Part 1)		SAC
3.33.	miTT2	VS1	Summary of Vital Signs (Part 2)		SAC
3.34.	miTT1	VS1	Summary of Change from Baseline in Vital Signs (Part 1)		SAC
3.35.	miTT2	VS1	Summary of Change from Baseline in Vital Signs (Part 2)		SAC
Immunogenicity					
3.36.	miTT	IMM1	Summary of Positive Immunogenicity Results	Can be kept as miTT overall	SAC

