
 Reporting for tables, figures and formal statistical analyses : 
 Planned time relative to dosing will be used in figures, summaries, statistical analyses and calculation of any derived parameters, unless otherwise stated. The impact of any major deviation from the planned assessment times and/or scheduled visit days on the analyses and interpretation of the results will be assessed as appropriate. Reporting for Data Listings: 
 Planned and actual time relative to study drug dosing will be shown in listings (Refer to IDSL Statistical Principle 5.05.1). Unscheduled or unplanned readings will be presented within the subject's listings. Visits outside the protocol defined time-windows (i.e. recorded as protocol deviations) will be included in listings but omitted from figures, summaries and statistical analyses. 	
Unscheduled Visits	

 Unscheduled visits will not be included in summary tables or figures, unless otherwise stated. All unscheduled visits will be included in listings. 	
Descriptive Summary Statistics	
Continuous Data	Refer to IDSL Statistical Principle 6.06.1
Categorical Data	N, n, frequency, %
Descriptive Summary Statistics (Log Transformed Data)	N, n, geometric mean, 95% CI of geometric mean, standard deviation (SD) of logged data and between geometric coefficient of variation ($CV_{b/w} (\%)$): $CV_b (\%) = \sqrt{(\exp(SD^2) - 1) * 100}$ 
(NOTE: SD is the SD of log transformed data)

Reporting of Pharmacokinetic Concentration Data	
Descriptive Summary Statistics	Refer to IDSL Statistical Principle 6.06.1 Assign zero to NQ values (Refer to GUI_51487 for further details)
Reporting of Pharmacokinetic Parameters	
Descriptive	N, n, geometric mean, 95% CI of geometric mean, standard deviation (SD)

CONFIDENTIAL

204987

Reporting Standards	
Summary Statistics (Log Transformed)	of logged data and [between and or within] geometric coefficient of variation (CV _{b/w} (%)) will be reported. [1] $CV_b (\%) = \sqrt{(\exp(SD^2) - 1) * 100}$ (SD = SD of log transformed data) [2] $CV_w (\%) = \sqrt{(\exp(MSE) - 1) * 100}$ (MSE = mean square error from mixed effect model of loge-transformed data).
Parameters Not Being Log Transformed	Tmax, first point, last point and number of points used in the determination of lambda_z for listings

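### Under the default reporting rule, an unscheduled post-dose ECG that meets a potential-clinical-importance threshold is listed but not counted by treatment in the ECG safety tables

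*SAP*

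**What the plan says.** Three statements in section 10.3.3 of the current RAP amendment bear on this. The earlier RAP reproduced after it has the same wording.

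- On visits: "Unscheduled visits will not be included in summary tables or figures, unless otherwise stated", and "All unscheduled visits will be included in listings".
- On readings, under the rules for data listings: "Unscheduled or unplanned readings will be presented within the subject's listings".
- On time, under the rules for tables, figures and formal analyses: "Planned time relative to dosing will be used in figures, summaries, statistical analyses and calculation of any derived parameters, unless otherwise stated".

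Section 10.4.1 foresees a row for any visit after baseline. A subject with both high and low values counts in both categories of that row, and the section adds: "This will also be applicable to relevant Potential Clinical Importance summary tables". It does not say whether unscheduled values feed the row.

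Section 10.5.1 puts all available data from withdrawn subjects into listings, but only their planned data into tables and figures.

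Section 10.11.5 lists the ECG tables. For PCI Tables 3.26 and 3.30 the only programming note is "Categories as per PCI details in Section 10.6.2". Tables 3.27 and 3.31 refer back to the same note, and findings Tables 3.22 and 3.23 have none.

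**The concern.** A PCI frequency table exists to show, by treatment, how many subjects crossed a fixed limit. For the ECG these limits include a QTc of 500 msec or more and a rise from baseline above 60 msec (section 10.6.2). An ECG taken outside the schedule usually has a reason behind it, so it is a reading a safety reviewer would want in that count.

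Hypoxia and exercise are the stress part of this study, and the schedule appears to plan no 12-lead ECG there. If the default rule is followed, the PCI table for a treatment can show no event while Listing 19 shows one. A reader who relies on the table would miss it.

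**Working it through.** The plan gives no figure to reproduce. The check sets the rules against the ECG schedule and then shows what one omitted event does to the count.

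**Step 1: where a 12-lead ECG is planned (section 10.1.1).** The columns are partly displaced. As far as they can be read, each treatment period has three marks: pre-dose, 15-45 minutes after the start of dosing, and the final assessment after 30 minutes' rest. Further ECGs fall at screening and follow-up. Chamber entry is about 30 minutes after treatment, and the 15-45 minute column stands before the chamber columns. That leaves none of the three in the chamber. Telemetry runs continuously, but no telemetry table, figure or listing is planned.

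**Step 2: what happens to an extra ECG.** Suppose a 12-lead ECG is recorded in the chamber, or unplanned at an early exit.

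| Rule | Listing | Summary table |
|---|---|---|
| 10.3.3, unscheduled visits | Yes | No, by default |
| 10.3.3, unplanned readings | Yes | Not addressed expressly |
| 10.3.3, planned time | Planned and actual time shown | No slot for a reading without a planned time |
| 10.5.1, withdrawn subjects | All data | Planned data only |
| 10.4.1, any-visit row | Not addressed | Silent on unscheduled values |
| 10.11.5, notes on six ECG tables | Not addressed | No exception |

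No line admits the reading to a table, and two lines keep it out by default or by construction. A programmer following the text would leave it out.

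**Step 3: where the event would still be seen.** Listing 18 gives all ECG values for subjects with a PCI value, Listing 19 the PCI values, and Listing 20 abnormal findings. The adverse event tables, which do not depend on visits, would include it only if it was reported as an adverse event.

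**Step 4: size, as illustration only.** Section 3.1 gives 11 subjects randomised in Part 1 and up to 14 planned for Part 2. Exact (Clopper-Pearson) 95% intervals use:

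- for 0/n, upper limit = 1 − 0.025^(1/n);
- for 1/n, lower limit = 1 − 0.975^(1/n), and the upper limit is the p at which P(X ≤ 1) = 0.025.

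| n | Event omitted | Event counted |
|---|---|---|
| 14 | 0/14 = 0% (0 to 23.2%) | 1/14 = 7.1% (0.2 to 33.9%) |
| 11 | 0/11 = 0% (0 to 28.5%) | 1/11 = 9.1% (0.2 to 41.3%) |

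These assume that every subject received the treatment in question. One Part 1 subject did not complete both periods, so one treatment may have 11 − 1 = 10. The intervals overlap widely. What changes is whether the table shows any event at all.

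**The case against.** The strongest reply is that the rule names visits, not readings. An extra ECG on a dosing day is an unplanned reading within a scheduled visit. The plan says such readings are listed and does not expressly keep them out of tables. The rule also yields wherever the plan says otherwise. The reporting standards and table shells that 10.3.3 and 10.11.5 refer to are not reproduced, and they might say otherwise. This stands in part: a reader might infer that these ECGs can never be counted, and the document does not support that. It supports exclusion by default, by inference from the planned-time rule and the absence of any exception. If the sponsor thinks the text is open, the same clarifying sentence is needed.

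Second, the signal is not lost. Listings of this size can be read in full, and for laboratory and vital-sign PCI values the plan relies on listings alone (Table 4). That is fair and limits the weight of the point. For the ECG, however, the plan chose by-treatment PCI tables, and those should be complete.

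Third, ECGs taken for cause are recorded under hypoxia or exercise at irregular times. Pooling them with resting ECGs can itself distort a comparison. This stands, and it is why the row proposed below is descriptive.

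Two further inferences should be resisted. One is that the omission biases the treatment comparison towards no difference. That holds only if such ECGs cluster on a harmful treatment, which nothing here shows. The other is that Part 1 already supplies an example, because "One subject did not complete both periods 1 and 2 due to withdrawal due to AE". The plan does not say that this event was cardiac or involved an ECG. Nor does it mention for-cause ECGs anywhere, so the triggering situation is a possibility, not an observed fact.

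**Conclusion.** The point holds as a gap in the safety count and should be corrected before database freeze. Followed as written, section 10.3.3 would leave an unscheduled post-dose ECG that meets a PCI threshold out of the by-treatment frequencies, while Listings 18 to 20 would show it. The size is at most a few subjects, but in groups of 11 and at most 14 one subject decides between a zero and a non-zero entry.

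The conclusion rests on three assumptions: the damaged schedule table has been read correctly, the external reporting standards contain no overriding rule, and unscheduled 12-lead ECGs do in fact occur. The PASP analysis, the oxygen saturation criterion and the by-timepoint ECG summaries are not affected.

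**What to change.** Add to section 10.3.3: *Exception: unscheduled and early-withdrawal post-dose ECGs are counted, under the treatment of the period in which they were taken, in an any-visit-post-baseline (worst value) row of the ECG findings and ECG PCI tables (3.22, 3.23, 3.26, 3.27, 3.30, 3.31). This row is added where the shell lacks it, with a footnote identifying counts that come from unscheduled readings.*

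Keep the by-timepoint rows and the PASP and saturation models on scheduled readings. The change concerns only how recorded ECGs are tabulated, not when they are taken.

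The cost is one sentence, one worst-value flag in the ECG program and, where needed, one extra row. Because unscheduled ECGs are unequally ascertained between subjects and treatments, the row should be read as descriptive. Its counts may be slightly less favourable than those from scheduled readings alone.

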10.4. Appendix 4: Derived and Transformed Data

10.4.1. General

Multiple Measurements at One Time Point

- Mean of the measurements will be calculated and used in any derivation of summary statistics but if listed, all data will be presented.
- If there are two values within a time window the value closest to the target day for that window will be used. If values are the same distance from the target then the mean will be taken.
- Subjects having both High and Low values for Normal Ranges at any post-baseline visits for safety parameters will be counted in both the High and Low categories of "Any visit post-baseline" row of related summary tables. This will also be applicable to relevant Potential Clinical Importance summary tables.

Study Day

- Calculated as the number of days from randomisation date :
 - Ref Date = Missing → Study Day = Missing
 - Ref Date < Randomisation Date → Study Day = Ref Date – Randomisation Date
 - Ref Date ≥ Randomisation Date → Study Day = Ref Date – (Randomisation Date) + 1

10.4.2. Study Population

Demographics

Age

- GSK standard IDSL algorithms will be used for calculating age where birth date will be imputed as follows:
 - Any subject with a missing day will have this imputed as day '15'.
 - Any subject with a missing date and month will have this imputed as '30th June'.
- Birth date will be presented in listings as 'YYYY'.

Body Mass Index (BMI)

- Calculated as **Weight (kg) / [Height (m)]²**

Extent of Exposure

- Number of days of exposure to study drug will be calculated based on the formula:

$$\text{Duration of Exposure in Days} = \text{Treatment Stop Date} - (\text{Treatment Start Date}) + 1$$
- Subjects who were randomized but did not report a treatment start date will be categorised as having zero days of exposure.

CONFIDENTIAL

204987

10.4.3. Safety

ECG Parameters
RR Interval

 IF RR interval (msec) is not provided directly, then RR can be derived as : 
 [1] If QTcB is machine read & QTcF is not provided, then : $RR = \left[\left(\frac{QT}{QTcB} \right)^2 \right] * 1000$ 
 [2] If QTcF is machine read and QTcB is not provided, then: $RR = \left[\left(\frac{QT}{QTcF} \right)^3 \right] * 1000$ If ECGs are manually read, the RR value preceding the measurement QT interval should be a collected value THEN do not derive.
Corrected QT Intervals

 When not entered directly in the eCRF, corrected QT intervals by Bazett's (QTcB) and Fridericia's (QTcF) formulas will be calculated, in msec, depending on the availability of other measurements. IF RR interval (msec) is provided then missing QTcB and/or QTcF will be derived as : $QTcB = \frac{QT}{\sqrt[4]{RR}} \quad QTcF = \frac{QT}{\sqrt[3]{RR}}$

Laboratory Parameters

 If a laboratory value which is expected to have a numeric value for summary purposes, has a non-detectable level reported in the database, where the numeric value is missing, but typically a character value starting with '<x' or '>x' (or indicated as less than x or greater than x in the comment field) is present, the number of significant digits in the observed values will be used to determine how much to add or subtract in order to impute the corresponding numeric value. 
 Example 1: 2 Significant Digits = '< x ' becomes x - 0.01 Example 2: 1 Significant Digit = '> x' becomes x + 0.1 Example 3: 0 Significant Digits = '< x' becomes x - 1

10.4.4. Pharmacodynamic and Biomarker

Biomarkers
RAS Peptides

 Ang II, Ang(1-5), Ang(1-7)
Disease Biomarker

 Surfactant Protein D
Variance stabilising transformations (e.g. taking natural logarithms of the observed responses) may be implemented on a per endpoint basis, if deemed necessary by the study statistician. If transformations are used the results will be reported on the back-transformed response scales.

CONFIDENTIAL

204987

10.5. Appendix 5: Premature Withdrawals & Handling of Missing Data

10.5.1. Premature Withdrawals

Element	Reporting Detail
General	
 Subject study completion (i.e. as specified in the protocol) was defined as any subject who completes all phases in the study including the follow-up visit. Withdrawn subjects will not be replaced in the study. All available data from subjects who were withdrawn from the study will be listed and all available planned data will be included in summary tables and figures, unless otherwise specified.

10.5.2. Handling of Missing Data

Element	Reporting Detail
General	
Missing data occurs when any requested data is not provided, leading to blank fields on the collection instrument :
 
 These data will be indicated by the use of a “blank” in subject listing displays. Unless all data for a specific visit are missing in which case the data is excluded from the table. Answers such as “Not applicable” and “Not evaluable” are not considered to be missing data and should be displayed as such.
Outliers	Any subjects excluded from the summaries and/or statistical analyses will be documented along with the reason for exclusion in the clinical study report.
PK	If dosing and/or sampling times are missing, the relevant concentrations will be deleted from the population PK and PK/PD analysis dataset and summarized in a deletion record listing. Samples listed as having no sample (NS), no result (NR) or insufficient sample (IS) will be excluded from the PK data set and also included in the deletion record listing. GSK2586881 concentrations below the lower limit of quantification (LLQ) for the assay will be reported as NQ (Below Quantification Limit). All NQ values will be set to “.” (missing) in the population PK and PK/PD dataset. Individuals with all plasma concentrations reported as NQ will be included in the data set.
Biomarkers	
Any values below the Lower Limit of Quantification (LLQ) will be assigned a value of $\frac{1}{2}$ LLQ for display purposes in Figures and for computation of summary statistics. Any values above the Upper Limit of Quantification (ULQ) will be assigned to the ULQ for display purposes in Figures and for computation of summary statistics. If multiple LLQ and /or ULQ values are available per assay (for example if multiple runs with different standard curves are utilised) then the LLQ and/or ULQ value used for the above imputation shall be the minimum of the available LLQs and/or the maximum of the ULQs.
 
If the number of LLQ (and/or ULQ) values is large for an individual biomarker then alternative analysis strategies may be required. “Large” is hard to define

CONFIDENTIAL

204987

Element	Reporting Detail
	prospectively and may depend upon the dataset in question but a general rule of thumb is if >30% of values are LLQ and/or ULQ. If "large" numbers of LLQ and/or ULQ values are observed methodologies to summarise and analyse the responses similar to those detailed in "Standards for the Handling of NQ impacted PK Parameters" (Respiratory DB and CPMS - 14 th December 2009) may be employed. Any such methodology will be documented in the statistical contributions to the clinical study report.

